2.4.1 Clinical Evaluations

- Medical history (interim)
- Physical examination, including weight, and vital signs (i.e., temperature, pulse, respiratory rate, and blood pressure); review of concomitant medications and symptoms/side effects; and, assessment of performance status

2.4.2 Peripheral Blood/Urine Laboratory Evaluations

NOTE: Results from outside NIH are accepted.

- Required within 3 days:
 - Urine and/or serum HCG in WOCBP
- Required within 14 days:
 - CBC with differential; reticulocyte count
 - Chemistry panels, including: Acute Care Panel (sodium, potassium, chloride, CO₂, glucose, BUN, creatinine), Mineral Panel (serum calcium, phosphate, magnesium and albumin), and Hepatic Panel (alkaline phosphatase, ALT, AST, total and direct bilirubin)
 - Others: LDH, Uric acid, Total protein, Beta-2 Microglobulin
 - Serum protein electrophoresis (SPEP) and immunofixation to assess for presence and quantity of monoclonal protein (M-protein). Random urine sample for protein electrophoresis (UPEP) and immunofixation to assess for monoclonal protein in the urine (Bence-Jones proteinuria). Collect a 24 hour urine sample if patient's serum monoclonal protein is < 1.0 g/dl.
 - Serum free light-chain studies
 - Quantitative serum immunoglobulins
 - Coagulation panel, including: PT/INR and aPTT
 - Thyroid function tests, including: thyroid stimulating hormone (TSH), total triiodothyronine (T3), free thyroxine (T4)
- Required within 28 days:
 - Lymphocyte Phenotype: T, B and NK cell subsets

2.4.3 Bone Marrow Biopsy and Aspirate Evaluations

- Histopathological evaluation on bone marrow aspirate and biopsy (DLM)

- Immunophenotyping of aberrant clonal plasma cells by multiparametric flow cytometry (LP: [name] Lab)
- Interphase FISH (Mayo Laboratories)

2.4.4 Imaging Studies

NOTE: The following required to be done at NIH.

- ¹⁸F-FDG PET/CT
- Diffusion Weighted Whole Body MRI (DW-MRI) (exception: patients with a contraindication or inability to perform due to administrative or logistical reasons) (MIP)
- Skeletal Survey (CC)

NOTE: Results from NIH only. In certain scenarios, at the discretion of the investigator, a CT chest, abdomen and pelvis may substitute or be in addition to the above diagnostic imaging modalities.

- Radiation therapy imaging for planning and treatment position verification purposes, per institutional standards and treating radiation oncologist (must be done locally by ROB).

2.4.5 Research Correlates

NOTE: See Section 5 for additional information.

2.4.6 Questionnaires/Patient-Reported Outcomes (PROs)

NOTE: See Section 5.3.6 and Appendix G

3 STUDY IMPLEMENTATION

3.1 STUDY DESIGN

This is a single-arm, open-label, single institution phase 2 study of avelumab in combination with hypofractionated radiation therapy (BavXRT) in up to 27 patients with relapsed/refractory multiple myeloma (RRMM) with extramedullary disease who have progressed on 2 or more prior lines of therapy. Avelumab monotherapy will continue after cycle 2 (concurrent avelumab and radiotherapy) until disease progression, unacceptable toxicity, or other criteria meeting stopping criteria (see Section 3.8).

The primary endpoint of ORR per IMWG criteria will be augmented with secondary endpoints including safety and tolerability of BavXRT and exploratory correlative studies.

All ongoing testing and procedures will take place per the Study Calendar (Section 3.7).

NOTE: Treatment is planned to be administered on an outpatient basis. At the investigator's discretion (e.g., for additional monitoring, patient social reasons, scheduling logistics, etc.), patients may be treated on an inpatient basis. Any cases of planned hospitalization are not considered reportable serious adverse events per Section 6.1.2.

[figure not shown]
[figure not shown]
3.1.1 Cycle 1 and 3 and beyond

- Patients will receive avelumab 800 mg IV every two weeks

3.1.2 Cycle 2 only

- Patients will receive XRT to at least one extramedullary plasmacytoma or lytic lesion daily for 5 days starting day 1.

- Patients will receive avelumab 800 mg IV every two weeks

3.2 DRUG ADMINISTRATION

3.2.1 Avelumab (MSB0010718C) Dosage

Patients will receive avelumab 800 mg IV over 60 minutes (+/- 20 minutes) on days 1 and 15 of each 28-day or 4-week cycle. If radiation therapy on Day 1 of Cycle 2 is delayed (+/- 5 days), subsequently, Day 15 of Cycle 2 will occur 14 days after. Any avelumab administration day may be adjusted +/- 5 days as needed due to scheduling or other administrative reasons. The maximum window between cycles is 14 days.

3.2.2 Avelumab Preparation

Visually inspect vial for particulate matter and discoloration. Avelumab is a clear, colorless to slightly yellow solution. Discard vial if the solution is cloudy, discolored, or contains particulate matter.

Withdraw the required volume of avelumab from the vial(s) and inject it into a 250 mL infusion bag containing either 0.9% Sodium Chloride Injection or 0.45% Sodium Chloride Injection.

Gently invert the bag to mix the diluted solution and avoid foaming or excessive shearing.

Inspect the solution to ensure it is clear, colorless, and free of visible particles.

Discard any partially used or empty vials.

3.2.3 Avelumab Administration

- **Infusion:** Administer the diluted solution over 60 minutes through an intravenous line containing a sterile, non-pyrogenic, low protein binding in-line filter (pore size of 0.2 micron). Do not co-administer other drugs through the same intravenous line.
- **Premedication:** To mitigate infusion related reactions, premedication with an antihistamine and paracetamol (acetaminophen) 30 to 60 minutes prior to the first 4 infusions of avelumab is mandatory (e.g., 25-50 mg diphenhydramine and 650 mg acetaminophen). At the discretion of the investigator, ranitidine 150 mg PO or IV 30-60 minutes prior to avelumab may also be administered. Premedication should be administered for subsequent avelumab infusions based upon clinical judgment and presence/severity of prior infusion reactions. This may be modified based on local treatment standards and guidelines, as appropriate.
- **Setting:** Avelumab should be administered in a setting that allows for immediate access to an intensive care unit or equivalent environment and administration of therapy for anaphylaxis, such as the ability to implement immediate resuscitation measures. Steroids (dexamethasone 10 mg), epinephrine (1:1,000 dilution), allergy medications (IV antihistamines), bronchodilators, or equivalents, and oxygen should be available for immediate access.
- **Observation period:** Following avelumab infusions, patients must be observed for 30 minutes post infusion for potential infusion related reactions. Infusions may be done peripherally or via central venous access device (not required by study), etc.

3.3 RADIATION THERAPY ADMINISTRATION

3.3.1 Personnel

Radiation therapy to extramedullary and/or lytic lesions will be administered by Radiation Oncology investigators from the Radiation Oncology Branch of the CCR/NCI/NIH.

3.3.2 Radiation Dosage and Schedule

At any given lesion, selected as a target for this study, 5 Gy per fraction will be delivered on 5 consecutive treatment days (although consecutive days are ideal, a treatment may be delayed up to 3 days for administrative purposes) for a total dose 25 Gy. Treatment will be administered on Cycle 2 Day 1-5 (+/- 7 days). Radiation Oncology Branch Associate Investigators will be the points of contact (1st: [name]; 2nd: [name]). Depending on the radiation field for a given lesion, alternate dosing and schedules will be allowed.

3.3.3 Radiation Sites

Only lesions which are safely amenable to radiation will be considered for radiation. Sites may include lytic or extramedullary lesions of the long bones, axial skeleton, and soft tissue. At the

discretion of the investigator, more than a single site may be irradiated if clinically indicated. Doses to critical structures, including spinal cord, bowel, kidneys, lungs, heart, and brain, will be limited to standard dose constraints that are known to be associated with lower than 2-5% average risk of long term radiation-related side effects. Lesions that normally would not have a clinical indication for radiation will not be irradiated. In addition, we will treat all lesions that clinically require it.

3.3.4 Additional Irradiation

At the discretion of the investigator, a patient may receive palliative radiation to additional sites of disease.

3.4 DOSE MODIFICATIONS

3.4.1 Avelumab

- Dose reductions are not allowed.
- Doses should be delayed in general for Grade ≥ 3 toxicity until toxicity resolves to Grade ≤ 1 unless otherwise stated in the protocol. Management should follow accepted medical and institutional standards.
- Dose delays should only be instituted for adverse reactions that are at least possibly due to (suspected) avelumab.
- Laboratory abnormalities which are clinically insignificant and/or unrelated to avelumab in the judgement of the investigator will not lead to dose delays.
- Grade 3 fatigue, local reactions, headache, nausea, emesis that resolves to Grade ≤ 1 with medical management will not lead to dose delays.
- Management guidelines for infusion-related adverse reactions are found in [Appendix B: Treatment Modification for Symptoms of Infusion-Related Reactions](#) and should be followed along with institutional standards.
- Immune-related adverse reactions (irAE) should lead to treatment modifications and management per [Appendix C](#).
- Patients may temporarily suspend study treatment for up to 28 days from the last dose if they experience toxicity that is considered related to the study drug and requires a dose to be held.
- Local tumor flare phenomenon defined as local pain, irritation, or rash localized at sites of known or suspected myelomatous lesions will not be considered adverse events or lead to dose interruptions.

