15.3 APPENDIX C: MANAGEMENT OF IMMUNE-MEDIATED ADVERSE REACTIONS

15.3.1 Gastrointestinal irAEs

Severity of Diarrhea/Colitis (NCI-CTCAE v5)	Initial Management	Follow-up Management

Grade 1
 
Diarrhea: increase < 4 stools/day over Baseline; mild increase in ostomy output compared to baseline
 
Colitis: a symptomatic
	
Continue a velumab therapy
 
Symptomatic treatment (e.g. loperamide)
	
Close monitoring for worsening symptoms
 
Educate subject to report worsening immediately
 
If worsens: Treat as Grade 2, 3 or 4.

Grade 2
 
Diarrhea: 4 to 6 stools per day over Baseline; moderate increase in ostomy output compared to baseline; limiting instrumental ADL IV fluids indicated < 24 hours; not interfering with ADL
 
Colitis: a abdominal pain; mucus or blood in stool
	
Withhold a velumab therapy
 
Symptomatic treatment
	
If improves to Grade ≤ 1: Resume a velumab therapy
 
If persists > 5-7 days or recurs: Treat as Grade 3 or 4.

Grade 3 to 4
 
Diarrhea (Grade 3): increase of ≥ 7 stools per day over Baseline; hospitalization indicated; severe increase in ostomy output compared to baseline; limiting self care ADL incontinence; IV fluids ≥ 24 h; interfering with ADL
 
Grade 4: Life-threatening consequences; urgent intervention indicated
 
Colitis (Grade 3): severe a abdominal pain, medical intervention indicated, peritoneal signs
 
Grade 4: life-threatening, urgent intervention indicated perforation
	
Withhold a velumab for Grade 3.
 
Permanently discontinue a velumab for Grade 4 or recurrent Grade 3.
 
1.0 to 2.0 mg/kg/day prednisone IV or equivalent
 
Add prophylactic antibiotics for opportunistic infections
 
Consider lower endoscopy
	
If improves: Continue steroids until Grade ≤ 1, then taper over at least 1 month; resume avelumab therapy following steroids taper (for initial Grade 3).
 
If worsens, persists > 3 to 5 days, or recurs after improvement: Add infliximab 5mg/kg (if no contraindication). Note: infliximab should not be used in cases of perforation or sepsis.

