15.3.2 Dermatological irAEs

Grade of Rash (NCI-CTCAE v5)	Initial Management	Follow-up Management

Grade 1 to 2 Covering ≤30% body surface area
	
Continue a velumab therapy Symptomatic therapy (for example, antihistamines, topical steroids)
	
If persists > 1 to 2 weeks or recurs: Withhold a velumab therapy Consider skin biopsy Consider 0.5-1.0 mg/kg/day prednisone or equivalent. Once improving, taper steroids over at least 1 month, consider prophylactic antibiotics for opportunistic infections, and resume a velumab therapy following steroids taper. If worsens: Treat as Grade 3 to 4.

Grade 3 to 4 Grade 3: Covering >30% body surface area; Grade 4: Life threatening consequences
	
Withhold a velumab for Grade 3. Permanently discontinue for Grade 4 or recurrent Grade 3. Consider skin biopsy Dermatology consult 1.0 to 2.0 mg/kg/day prednisone or equivalent Add prophylactic antibiotics for opportunistic infections
	
If improves to Grade ≤ 1: Taper steroids over at least 1 month; resume a velumab therapy following steroids taper (for initial Grade 3).

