15.3.5 Renal irAEs

Grade of Creatinine Increased (NCI-CTCAE v5)	Initial Management	Follow-up Management

Grade 1 Creatinine increased >ULN to 1.5 x ULN
	
Continue avelumab therapy
	
Continue renal function monitoring If worsens: Treat as Grade 2 to 3 or 4.

Grade 2 to 3 Creatinine increased > 1.5 and ≤ 6 x ULN
	
Withhold avelumab therapy Increase frequency of monitoring to every 3 days 1.0 to 2.0 mg/kg/day prednisone or equivalent. Add prophylactic antibiotics for opportunistic infections Consider renal biopsy
	
If returns to Grade ≤1: Taper steroids over at least 1 month, and resume avelumab therapy following steroids taper. If worsens: Treat as Grade 4.

Grade 4 Creatinine increased > 6 x ULN
	
Permanently discontinue avelumab therapy Monitor creatinine daily 1.0 to 2.0 mg/kg/day prednisone or equivalent. Add prophylactic antibiotics for opportunistic infections Consider renal biopsy Nephrology consult
	
If returns to Grade ≤1: Taper steroids over at least 1 month.

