15.3.8 Other irAEs

NOTE: This pertains to “other” irAEs (i.e., not described above).

Grade of other irAEs (NCI-CTCAE v5)	Initial Management	Follow-up Management
Grade 2 or Grade 3 clinical signs or symptoms suggestive of a potential irAE	Withhold a velumab therapy pending clinical investigation	If irAE is ruled out, manage as appropriate according to the diagnosis and consider re-starting a velumab therapy If irAE is confirmed, treat as Grade 2 or 3 irAE.
Grade 2 irAE or first occurrence of Grade 3 irAE	Withhold a velumab therapy 1.0 to 2.0 mg/kg/day prednisone or equivalent Add prophylactic antibiotics for opportunistic infections Specialty consult as appropriate	If improves to Grade \leq 1: Taper steroids over at least 1 month and resume a velumab therapy following steroids taper.
Recurrence of same Grade 3 irAEs	Permanently discontinue a velumab therapy 1.0 to 2.0 mg/kg/day prednisone or equivalent Add prophylactic antibiotics for opportunistic infections Specialty consult as appropriate	If improves to Grade \leq 1: Taper steroids over at least 1 month.
Grade 4	Permanently discontinue a velumab therapy 1.0 to 2.0 mg/kg/day prednisone or equivalent and/or other immunosuppressant as needed Add prophylactic antibiotics for opportunistic infections Specialty consult.	If improves to Grade \leq 1: Taper steroids over at least 1 month
Requirement for 10 mg per day or greater prednisone or equivalent for more than 12 weeks for reasons other than hormonal replacement for adrenal insufficiency Persistent Grade 2 or 3 irAE lasting 12 weeks or longer	Permanently discontinue a velumab therapy Specialty consult	

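### The 28-day limit on holding avelumab in section 3.4.1 conflicts with the Appendix C routes that resume it only after a steroid taper of at least one month, and nothing says which prevails

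*Combined protocol and SAP*

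**What the plan says.** Section 3.4.1 lists the rules for delaying avelumab. One bullet says "Patients may temporarily suspend study treatment for up to 28 days from the last dose", and its scope is "toxicity that is considered related to the study drug and requires a dose to be held". It has no carve-out for irAEs. Another bullet in the same list says that irAEs "should lead to treatment modifications and management per" Appendix C.

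Appendix C ties resumption to a completed steroid taper of at least one month on these routes:

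- initial Grade 3 diarrhea or colitis (15.3.1);
- persistent or recurrent Grade 1 to 2 rash treated with steroids, and initial Grade 3 rash (15.3.2);
- Grade 2 pneumonitis (15.3.3);
- Grade 2 to 3 creatinine increase (15.3.5), where the wording is "Taper steroids over at least 1 month, and resume avelumab therapy following steroids taper";
- other Grade 2 or first Grade 3 irAEs (15.3.8).

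Appendix C also has its own time limits for permanent discontinuation. One of them is "Persistent Grade 2 or 3 irAE lasting 12 weeks or longer"; the other is a steroid requirement lasting more than 12 weeks. Section 3.8.1 lists unacceptable toxicity as a reason for removal from therapy but says nothing about a hold that runs past a limit.

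**The concern.** An irAE attributed to avelumab that requires a held dose falls under both bullets of 3.4.1. One allows 28 days from the last dose. The other leads to an appendix whose instructions take longer than that. Whether a patient recovering from an immune toxicity is given avelumab again then depends on which passage the investigator follows. That is a question of patient safety and of consistent conduct, and the protocol should answer it in one way.

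**Working it through.** **Inputs**

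- Limit: L = 28 days from the last dose (3.4.1).
- Taper: at least one month, completed before resumption (15.3.1, 15.3.2, 15.3.3, 15.3.5, 15.3.8). The protocol does not define a month in days, so m is taken as 28, 30 or 31.
- Dosing on days 1 and 15 of a 28-day cycle (3.2.1), so a hold of 28 days from the last dose allows one missed dose.
- a = days from the last dose to the hold and the start of steroids; b = days on steroids until the event has improved enough for the taper to start. The protocol fixes neither; the values below are illustrations.

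**Earliest restart, in days from the last dose: t = a + b + m**

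| a, b | m = 28 | m = 30 | m = 31 |
|---|---|---|---|
| 0, 0 | 28 | 30 | 31 |
| 1, 1 | 30 | 32 | 33 |
| 7, 7 | 42 | 44 | 45 |

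The room left for onset and improvement is L − m = 0, −2 or −3 days. The limit is met only with a 28-day month and a taper that begins on the day of the last dose. Appendix C rules that out in practice, because the event must first appear and improve on steroids. With one day for each step the restart is 2 to 5 days over the limit; with a week for each it is 14 to 17 days over.

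**Sensitivity to how the limit is read**

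- Adding the 5-day administrative window of 3.2.1 gives 28 + 5 = 33 days and leaves 5, 3 or 2 days for a + b. That window is for scheduling, not toxicity.
- Counting 28 days from the first missed dose gives 14 + 28 = 42 days and leaves 14, 12 or 11 days. The text counts from the last dose.

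**Contrast with Appendix C's own limits:** 12 weeks × 7 = 84 days, three times 28.

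**How many patients**

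Section 1.2.8 gives pooled avelumab rates (N = 1738). The non-rash irAEs that could reach a taper-then-resume route are colitis 1.5%, pneumonitis 1.2%, myositis 0.5%, and nephritis, uveitis and Guillain-Barré syndrome at 0.1% each:

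1.5 + 1.2 + 0.5 + 0.1 + 0.1 + 0.1 = 3.5%, and 27 × 0.035 = 0.945, about 0.9 patients.

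This counts every case of any grade as tapered and resumed, so it is an upper figure for the expected number at those rates. Hepatitis is left out because Grade 2 resumes on improvement and Grade 3 to 4 is discontinued (15.3.4). Endocrine events are left out because they resume on improvement (15.3.7). Immune-related rash (5.2%) would add up to 27 × 0.052 = 1.4 patients, but Grade 1 to 2 rash initially continues avelumab and steroids are only to be considered if it persists, so the share that counts is unknown.

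**The case against.** The best defence is that Appendix C is the specific rule for irAEs. The bullet that refers irAEs to it stands just before the 28-day bullet, and Appendix C has its own 12-week limits. On that reading the 28-day limit governs other related toxicity and every passage has effect. This is workable, and many sites would probably read it so, but the protocol does not say it. The phrase in 3.4.1 that yields to other protocol provisions belongs to the bullet on delaying for Grade 3 or higher toxicity, not to the 28-day bullet.

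A reader might also infer more than the documents support:

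- **That the patient must stop.** The 28-day bullet is permissive, no passage makes a longer hold a permanent discontinuation, and 3.8.1 does not list one. Only the instruction to resume is explicit.
- **That every steroid-treated irAE is caught.** Grade 2 diarrhea or colitis and Grade 2 liver elevation that settle without steroids, and Grade 3 to 4 endocrinopathy, resume on improvement. Treated hypophysitis has a taper of at least a month, but resumption depends on improvement (and on pituitary shrinkage if the MRI was abnormal), not on finishing the taper. These can fall within 28 days.
- **That section 3.2.1 adds a third limit.** It does say "The maximum window between cycles is 14 days", but footnote 3 of the Study Calendar (section 3.7) confines that window to scheduling or other administrative reasons. It is not a limit on toxicity holds.
- **That the primary result is at risk because four responders decide it.** Best response runs from the start of treatment to progression (6.3.1), patients who stop for other reasons are followed until progression (3.6.3), and all dosed patients are in the analysis population (10.3). Median first irAE onset is 11.7 weeks (1.2.8), after the Cycle 2 radiotherapy. Nothing in the documents shows a change in the number of responders.

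**Conclusion.** The contradiction stands for the taper-then-resume routes of Appendix C: both stated rules cannot be followed, and no passage sets precedence. It is an internal inconsistency, wrong as written, and should be corrected because it concerns re-exposure after an immune toxicity.

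Its expected reach is small: about 0.9 of 27 patients at most from non-rash irAEs, plus an unknown share of rash. That figure assumes that pooled single-agent rates, from a solid-tumour population, carry over to avelumab with radiotherapy in myeloma. It also leaves out events for which section 13.1.2 gives only an incidence below 1%, such as pancreatitis. The finding itself does not depend on this estimate, since the day arithmetic holds for any patient on these routes.

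**What to change.** Reconcile section 3.4.1 with Appendix C sections 15.3.1, 15.3.2, 15.3.3, 15.3.5 and 15.3.8. State in 3.4.1 whether the 28-day limit applies to holds managed under Appendix C, and how it relates to the 12-week limits in 15.3.8. State in 3.8.1 what follows when the applicable limit is exceeded. Section 3.2.1 needs no change for this purpose. Which limit is right is a clinical decision for the sponsor. The cost is a wording amendment; the design, sample size and analysis are unaffected.

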6 DATA COLLECTION AND EVALUATION

6.1 DATA COLLECTION

6.1.1 Summary

The PI will be responsible for overseeing entry of data into an in-house password protected electronic system (C3D) and ensuring data accuracy, consistency and timeliness. The principal investigator, associate investigators/research nurses and/or a contracted data manager will assist with the data management efforts. All data obtained during the conduct of the protocol will be

kept in secure network drives or in approved alternative sites that comply with NIH security standards. Primary and final analyzed data will have identifiers so that research data can be attributed to an individual human subject participant.

All adverse events, including clinically significant abnormal findings on laboratory evaluations, regardless of severity, will be followed until return to baseline or stabilization of event.

Document AEs from the first study intervention, Study Day 1 through 90 days after last treatment. Beyond the 90 day period after the last drug was administered, only adverse events which are serious and related to the study intervention need to be recorded.

End of study procedures: Data will be stored according to HHS, FDA regulations, and NIH Intramural Records Retention Schedule as applicable.

Loss or destruction of data: Should we become aware that a major breach in our plan to protect subject confidentiality and trial data has occurred, this will be reported expeditiously per requirements in section 7.2.1.

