6.1.2 Data Collection/Recording Exceptions

6.1.2.1 Abnormal Laboratory Values

An abnormal laboratory value will be recorded in the database as an AE **only** if the laboratory abnormality is characterized by any of the following:

- Results in discontinuation from the study
- Is associated with clinical signs or symptoms
- Requires treatment or any other therapeutic intervention
- Is associated with death or another serious adverse event, including hospitalization.
- Is judged by the Investigator to be of significant clinical impact
- If any abnormal laboratory result is considered clinically significant, the investigator will provide details about the action taken with respect to the test drug and about the patient's outcome.

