6.1.2.2 Hospitalizations

Any cases of planned or prolonged hospitalization are not considered reportable serious adverse events if for the following reasons:

- Closer monitoring and/or prophylaxis of TLS at any cycle

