8 SPONSOR SAFETY REPORTING

8.1 DEFINITIONS

8.1.1 Adverse Event

Any untoward medical occurrence in a patient or clinical investigation subject administered a

pharmaceutical product and which does not necessarily have a causal relationship with this treatment. An adverse event (AE) can therefore be any unfavorable and unintended sign (including an abnormal laboratory finding), symptom, or disease temporally associated with the use of a medicinal (investigational) product, whether or not related to the medicinal (investigational) product (ICH E6 (R2))

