8.1.5 Relationship to Study Product

All AEs will have their relationship to study product assessed using the terms: related or not related.

- Related – There is a reasonable possibility that the study product caused the adverse event. Reasonable possibility means that there is evidence to suggest a causal relationship between the study product and the adverse event.

- Not Related – There is not a reasonable possibility that the administration of the study product caused the event.

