8.2 ASSESSMENT OF SAFETY EVENTS

AE information collected will include event description, date of onset, assessment of severity and relationship to study product and alternate etiology (if not related to study product), date of resolution of the event, seriousness and outcome. The assessment of severity and relationship to the study product will be done only by those with the training and authority to make a diagnosis and listed on the Form FDA 1572 as the site principal investigator or sub-investigator. AEs occurring during the collection and reporting period will be documented appropriately regardless of relationship. AEs will be followed through resolution.

SAEs will be:

- Assessed for severity and relationship to study product and alternate etiology (if not related to study product) by a licensed study physician listed on the Form FDA 1572 as the site principal investigator or sub-investigator.
- Recorded on the appropriate SAE report form, the medical record and captured in the clinical database.
- Followed through resolution by a licensed study physician listed on the Form FDA 1572 as the site principal investigator or sub-investigator.

For timeframe of recording adverse events, please refer to section **6.1**. All serious adverse events recorded from the time of first investigational product administration must be reported to the sponsor with the exception of any listed in section **8.5**.

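### Section 3.4.1 declares local pain, irritation or rash at a myeloma site not to be an adverse event, without any limit, against the protocol's own AE definition in 8.1.1, so such events can drop out of the safety endpoint

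*Combined protocol and SAP*

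**What the plan says.** Section 3.4.1 (dose modifications for avelumab) defines local tumor flare by three symptoms (pain, rash or irritation, all local). Events of this kind "localized at sites of known or suspected myelomatous lesions will not be considered adverse events or lead to dose interruptions". The sentence does two things: it removes AE status, and it says the events do not interrupt dosing. An earlier bullet in the same list, beginning "Grade 3 fatigue, local reactions, headache, nausea, emesis that resolves to Grade", is limited by grade and by resolution, and it concerns dose delays only.

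Elsewhere the protocol says:

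- Section 8.1.1: "An adverse event (AE) can therefore be any unfavorable and unintended sign (including an abnormal laboratory finding), symptom, or disease temporally associated" with use of the product, whether or not related to it.
- Section 6.1.1: all AEs, "regardless of severity, will be followed until return to baseline or stabilization of event".
- Section 8.2: "AEs occurring during the collection and reporting period will be documented appropriately regardless of relationship".
- Section 8.1.5: "All AEs will have their relationship to study product assessed using the terms: related or not related".
- Section 6.1.2, the section for recording exceptions, has two entries. One sets conditions under which "An abnormal laboratory value will be recorded in the database as an AE". The other covers hospitalization for "Closer monitoring and/or prophylaxis of TLS at any cycle". Lesion-site flare is in neither.
- Section 3.4.2 (radiation) calls rash and pain local toxicity. It says flare may appear within days of radiation and is typically self-limited. It contains no AE exclusion.

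The safety endpoint in Section 10.1 is a count of AEs (all grades, Grade 3-4 and serious). Section 10.4.3 summarizes tolerability descriptively in terms of AEs.

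**The concern.** An AE exclusion with no bounds sits in a dose-modification list, away from both the AE definition and the list of recording exceptions. A site that follows 3.4.1 would not enter a Grade 3 painful reaction at the irradiated lesion, even if the investigator thought it treatment-related. A site that follows 8.1.1 would enter it.

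Every patient is to receive radiation to at least one such lesion in cycle 2 (Section 3.1.2), so the exclusion covers the place where local toxicity of the combination is most likely to show. The safety and tolerability of that combination is a secondary objective. A serious event could also be affected, because the SAE definition in Section 8.1.2 starts from an adverse event or a suspected adverse reaction.

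**Working it through.** **Text comparison**

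1. *What limits the exclusion?* Flare is defined in 3.4.1 by three symptoms and a site. There is no grade, seriousness, attribution or time limit, and the site need not be irradiated. The label adds no restriction beyond its own definition.
2. *Does it conflict with the AE definition?* New local pain or rash during treatment is an unfavorable and unintended symptom or sign temporally associated with the product, so it is an AE under 8.1.1 and not an AE under 3.4.1. The conflict is direct.
3. *Do 6.1.1, 8.2 and 8.1.5 conflict too?* Only through step 2. They say how an AE is followed, documented and attributed once it is an AE. They show that neither low severity nor unrelatedness is a reason for omission.
4. *Is it a listed exception?* No. Section 6.1.2 covers laboratory values and hospitalization related to TLS.
5. *Can treatment-related events fall inside it?* Yes. Section 3.4.2 links flare to radiation and calls the same symptoms toxicity.
6. *Do the exclusions in 10.4.4 cover it?* No. They drop clinically insignificant, conservatively resolved or unrelated AEs from the stopping rule only. Those events remain AEs for 10.1 and 10.4.3.

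**What one omitted patient is worth**

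The weight is 1/n, where n is the number of patients in the denominator.

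| n | Source | 1/n |
|---|---|---|
| 27 | planned evaluable total, Section 10.2 | 3.7 points |
| 30 | accrual ceiling, Section 10.2 | 3.3 points |
| 13 | stage 1 only, Section 10.2 | 7.7 points |

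The 10.4.4 rule triggers at two events in the first 6 patients, or later at a cumulative fraction of 33% or more. One patient can decide it:

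- 2/6 = 33.3% suspends accrual; 1/6 = 16.7% does not.
- 9/27 = 33.3% meets the rule; 8/27 = 29.6% does not.

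**Illustration for the stopping rule**

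Starting rate: Section 1.2.8 gives 177 of 1738 patients on avelumab alone with a Grade ≥3 treatment-related event, and 177/1738 = 10.2% reproduces. To this I add an assumed 1, 2 or 3 points of countable lesion-site events. The documents give no such figure.

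The rule is read as counting patients, and patients are taken as independent. It triggers at 2 or more affected among the first 6, or, for n = 7 to 27, when affected/n ≥ 0.33. The probability for the first 6 is 1 − (1−p)^6 − 6p(1−p)^5. Later looks are added by exact recursion, patient by patient.

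| Rate p | Trigger within first 6 | Trigger by patient 27 |
|---|---|---|
| 10.2% (lesion-site events lost) | 0.118 | 0.135 |
| 11.2% | 0.139 | 0.160 |
| 12.2% | 0.160 | 0.187 |
| 13.2% | 0.182 | 0.2155 |

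Under these assumptions, losing the added events lowers the chance of a safety suspension from about 16%, 19% or 22% to about 13%.

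**The case against.** The strongest reply is that flare is a narrow, deliberate carve-out. It names a recognized local phenomenon, covers three symptoms only, and leaves fracture, neurologic, lung, bowel and blood events untouched. Section 3.4.2 lists local toxicity and flare in separate bullets, which suggests the authors saw two categories. Much lesion-site pain will predate treatment: Section 1.2.3 puts bone pain at 70–80% as a result of bone disease. Symptoms are still assessed at treatment visits (Section 3.7), and PROMIS asks about pain.

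Part of this stands. The reach is limited to pain, irritation and rash, and some of it is baseline disease. The loss is in the AE tabulation, not in all symptom data. But nothing in the text separates flare from local toxicity, since the definition of flare covers the same pain and rash. PROMIS pain items are not tied to a site and are not CTCAE-graded.

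The stopping-rule figures are open to challenge. The starting rate comes from avelumab alone in other tumors and is taken before the 10.4.4 exclusions. The added points are assumed. Both limbs of 10.4.4 speak of toxicity, so local events might be counted there despite 3.4.1. Its exclusion sentence is written in terms of AEs, however, so the point is not settled. At 9/27 the planned enrollment is already complete, so that boundary has little practical effect. These objections reduce the weight of the stopping-rule argument but do not remove the conflict over AE status.

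**Conclusion.** The concern holds. Section 3.4.1 contradicts 8.1.1 on whether these events are AEs, is not among the exceptions in 6.1.2 and, if followed, under-reports local events at the irradiated sites in the secondary safety endpoint. It permits omission without proving it, since a site applying 8.1.1 might still record them.

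The size is unknown because no lesion-site event rate is given. The per-patient weight is 3.7 points at n = 27. The effect on 10.4.4 is probably small and rests on assumed rates. The response endpoint and the two-stage design are not affected. This should be corrected, but it does not threaten the primary conclusion.

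**What to change.** In the flare bullet of 3.4.1, delete the five words *be considered adverse events or*. The sentence then says only that these events do not lead to dose interruption. The dosing wording is unchanged, and no position is taken on it here.

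Record these events as AEs, grade them by CTCAE v5 and assess relatedness as 8.1.5 already requires. Let those of Grade ≥3 enter the 10.4.4 count under its existing exclusions.

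A separate, minor wording point in 10.4.4: the first limb counts toxicities and the second a cumulative fraction. Since 2/6 = 33.3%, patients are evidently meant, yet read literally one patient with two events (1/6 = 16.7%) would suspend accrual. State that both limbs count patients and leave the thresholds as they are.

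The cost is one deletion, one clarification, a few more AE records and slightly higher reported AE rates.
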